Our core focus is on recording past diagnoses, and using the CANSAS-P to identify areas of need, and if they have been met. We have also included the AUDIT-C, DAST-10 and CORE-10 as these provide additional information by indicating severity of need in key areas. This will inform probation practice (for example cut-off scores on the CORE-10 can be used to indicate a need for referral to primary [6+] or secondary care [10+]), and enable assessment of the relationship between level of need and whether or not the need has been met - providing useful data for service commissioners and providers.

Online/telephone interviews will be based on a semi-structured interview guide to ascertain feedback on what it was like to implement the survey and if/how this could be incorporated into routine practice.

DEVELOPING QUALITY INDICATORS

Individuals participating in the service user panel will be asked to complete a consent form, and to contribute to a focus group in which they will be asked to describe positive and negative experiences of accessing care, and discuss what they think probation should know about their health, what they think the characteristics of excellent care are, and how this could be measured. The focus group will either take place at an appropriate location selected by Revolving Doors or using Microsoft Teams.

Individuals participating in the expert panel will be asked to complete a consent form (provided online at the start of the surveys), and to complete two online surveys. The first survey will ask them what they think the characteristics of excellent health and social care for people on probation are, and how this could be measured (i.e. what they think good quality indicators would look like). The second survey will ask them to rate a draft set of quality indicators on a 5-point Likert scale based on whether or not they have a clear link to outcomes for service users, can be a departure point for improvement actions, and are practical to implement. They will also be asked to state if they feel that anything is missing. Finally, these individuals will participate in a discussion of the final quality indicators to inform the research team of any final changes that may be needed. This will take place at the University of Lincoln and/or via teleconference/Microsoft Teams to suit participants.

SCHEDULE OF PROCEDURES

Informed consent will be taken for each element of the study. Each element will only occur once as follows:

- Survey on health and social care needs: exact timing is dependent on the stage that probation is at on their roadmap to recovery from the pandemic, but is likely to be over a period of three months between months 3 and 9 of the overall project
- Service user panel: month 7
- Expert panel survey one: month 2
- Systematic review: months 1-8
- Expert panel survey two: months 11-12
- Final discussion of quality indicators: month 16

WITHDRAWAL

Participants can withdraw from any element of the study at any time. For all of the surveys (of service users and the expert panel), data will be collected anonymously. Therefore, participants will be made aware (via the information sheet and consent form) that should they withdraw the data collected to date may not be erased in accordance with the University's Research Privacy Notice and information given in the Participant Information Sheet and may still be used in the final analysis.

ETHICAL AND REGULATORY CONSIDERATIONS

ASSESSMENT AND MANAGEMENT OF RISK

We do not anticipate that taking part in this study will cause any pain, discomfort, or changes to lifestyle for participants. The burden involved will simply be the time to complete a survey/participate in a focus group (service user panel)/complete a survey and rate quality indicators (expert panel). It is possible that reflecting on health needs or past experiences around accessing healthcare may cause distress. Steps have been taken to minimise the burden by keeping the questions asked in each of these elements to a minimum and advising participants that it is up to them what they answer and how they answer – they do not need to share anything too upsetting.

The participant information sheets will make it clear that should someone discuss plans to harm their self/another, or commit a criminal offence, appropriate persons (probation staff) will be aware of this as probation staff will be directly administering the surveys, or giving them out for self-completion, and looking at the participants' answers straight afterwards. Surveys will only be administered in an appropriate space – so if conducted by phone or online (e.g. via Microsoft Teams), a participant will need to have an appropriate (private) space in which to take part.

Page 21 of 25

It will be made clear to focus group participants that they do not need to discuss any past experience that they may find upsetting, and questions will be designed so that this is unlikely to occur. In the event that an individual did become upset, they will be told that they can take a break, or leave the group. All participants will receive a debrief sheet containing details of support services.

Individual participant medical information obtained as a result of this study are considered confidential and disclosure to third parties is prohibited with the exceptions noted. Medical information may be given to the participant's medical team and all appropriate medical personnel responsible for the participant's welfare.

If information is disclosed during the study that could pose a risk of harm to the participant or others, the researcher will discuss this with the CI and where appropriate report accordingly.

ADVERSE EVENTS

Due to the nature of this study, no adverse events are anticipated and no adverse event data will be collected.

ETHICS REVIEW AND COMPLIANCE

The study shall not commence until the study protocol, information sheets and consent forms have been reviewed and approved from a Research Ethics Committee and relevant probation ethics permission is obtained

The sponsor will be responsible for deciding whether amendments are substantial and non-substantial in collaboration with the Chief Investigator.

Where an amendment is required to study documentation that required REC approval, changes will not be implemented until REC approval is received. Where an amendment requires local approval this shall be sought prior to the amendment be implemented at each site in accordance with the approval letter.

Should an amendment be required to eliminate an apparent immediate hazard to participants this may be implemented immediately and the REC and the NRC will be notified as soon as possible.

Minor amendments for logistical or administrative purposes may be implemented immediately

Amendments will be logged on the Sponsor's Study Amendment Log and stored in the Trial Master/Site File(s).

Annual Progress Reports shall be submitted to the REC within 30 days of the anniversary date on which the favourable opinion was given – until the end of the study.

A final report shall (where possible) be submitted to the REC within one year after the end of the study.

If the study is terminated prematurely the CI will notify the REC, including the reasons for premature termination.

PEER REVIEW

The proposal for this study was reviewed internally at the University of Lincoln, and in addition was reviewed by the Research Design Service, and the NIHR funding committee.

PUBLIC & PATIENT INVOLVEMENT

The need for this research was partly informed by information provided by participants in our previous research in this area. Service users and probation staff have been involved in developing and focusing our funding application for the project. They have supported the researchers in developing participant information sheets, invitation letters and consent forms and an interview schedule. The survey has been piloted with people with lived experience of the criminal justice system.

An expert panel including probation staff, and a service user panel will contribute to the development of quality indicators. Here, people with lived experience of the criminal justice system will be recruited by Revolving Doors staff and Peer Researchers. In a focus group co-facilitated by the Peer Researchers, participants will be invited to share their experiences of accessing care.

A service user and probation staff will also be part of the steering group and contribute to dissemination of findings, including producing an easy-read summary of findings, and attending sessions on writing for publication if desired.

PROTOCOL COMPLIANCE

Accidental protocol deviations may occur at any time. Accidental protocol deviations will be adequately documented on the relevant forms and reported to the Chief Investigator and Sponsor immediately.

Deviations from the protocol which are found to frequently recur are not acceptable, these will require immediate action and could potentially be classified as a serious breach.

DATA PROTECTION AND PATIENT CONFIDENTIALITY

All study staff and investigators will comply with the principles of the Data Protection Act (2018) in protecting the rights of study participants with regards to the collection, storage, processing and disclosure of personal information and will uphold the Act's/Regulations core principles.

No personal data will be included in our publications - responses in all elements of the research will be anonymised (e.g. through appropriate word replacement in text during transcription of the focus group) and/or reported at aggregate level.

Individuals participating in the service user and expert panels will be asked whether they would like their name, or the name of the organisation that they are based with, to be included in acknowledgments sections of any publications/presentations from the research as appropriate. This will be part of the participant information resources.

Data will be stored on the University network, in an area of a shared drive that is only accessible to the research team, and/or on OneDrive. Hard copies of participant consent forms and surveys will be stored in locked metal filing cabinets.

Data generated as a result of this study will be available for inspection on request by the participating physicians, the University of Lincoln representatives, the REC, NRC and the regulatory authorities. Anonymised data may also be added to a repository at the end of the study. This will be made clear on the participant information resources.

INDEMNITY

The University of Lincoln as research Sponsor indemnifies its staff, research participants and research protocols with both public liability insurance and clinical trials insurance.

ACCESS TO THE FINAL DATASET

Members of the research team, including Revolving Doors Peer Researchers, will have access to the final dataset. Anonymised data will also be added to the University of Lincoln institutional repository and/or an external repository.

DISSEMINATION POLICY

The data custodian will be the Chief Investigator on behalf of the University of Lincoln.

During months 18-19, we will produce

- A report for NIHR
- An easy read summary
- Journal articles on the health and social care needs of people on probation, their patterns and experiences of service access, and the development of quality indicators.

We will make the final set of quality indicators freely available to the National Probation Service, and further disseminate them through members of the expert group, a blog site for the project, social media the Probation Institute, and the Confederation of European Probation.

The tools used within the surveys will also be available to the National Probation Service for future use.

Authorship eligibility guidelines and any intended use of professional writers

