- a. A systematic review of the literature to identify existing quality indicators for health and social care in use in probation outside of England, or elsewhere in the criminal justice system
- b. A service user panel focus group with individuals with lived experience of the criminal justice system to support the development of quality indicators
- c. Two online surveys with an expert panel of people working in the health and justice field. The first of these will ask participants what they think the characteristics of excellent health and social care for people on probation are, and how this could be measured (i.e. what they think good quality indicators would look like). The second survey will ask participants to rate a draft list of quality indicators compiled based on the findings from the systematic review, service user, and expert panels. The expert panel will be asked to rate these quality indicators on a 5-point Likert scale based on whether or not they have a clear link to outcomes for service users, can be a departure point for improvement actions, and are practical to implement. A mean score will be derived for each indicator. Participants will also be able to suggest additional indicators if they feel that something is missing
- d. Finally, the expert panel will discuss the final list of quality indicators developed from the study to enable any final amendments to be made if needed.

DATA ANALYSIS

Surveys of health and social care needs and the extent to which they are being met by current service provision: data will be entered into a database by a Research Assistant for analysis by the Medical Statistician. Analysis is anticipated to take place in SPSS and STATA. Demographic data will be used to determine the extent to which survey respondents reflect the population within the national probation caseload. The survey data will be weighted to better represent the national population in terms of its demographic profile using an appropriate weighting methodology propensity score weighting. Data will be analysed using descriptive statistics to show a) the prevalence of needs, and b) patterns of service access and the extent to which needs are being met. Mixed effects models (also known as multilevel models) will be used to predict health and social care needs based on service user and area characteristics.

Systematic review: Existing quality indicators will be extracted from the included papers for inclusion in the online surveys.

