Service user panel focus group: Participants will be interviewed using a semi-structured interview guide co-designed by the Peer Researchers. The focus group will be conducted online and recorded, transcribed verbatim, and analysed by the research team in NVivo using thematic analysis with support from the Peer Researchers.

Online surveys for development of quality indicators: Data from the first survey will be entered into NVivo (qualitative data analysis software) and analysed using thematic analysis. Ratings from the second survey will be extracted into a database for analysis. This will simply involve calculating the mean score for each indicator.

Draft analyses will be presented at project steering groups, with additional work, or revisions being undertaken if needed following discussion at these meetings.

Notes will be taken in Word during the discussion of the final draft indicators, and used to inform any final changes to them.

STUDY SETTING

Surveys of health and social care needs and the extent to which they are being met by current service provision: Data will be collected across four probation Local Delivery Units containing a mixture of urban and rural areas. Feedback will be collected from probation staff via online/telephone interviews.

Systematic review: Will be conducted at the University of Lincoln.

Service user panel focus group: Participants will recruited by Revolving Doors Agency peer researchers, and the focus group will take place online or at a location selected by Revolving Doors Agency.

Page 13 of 25

Online surveys for development of quality indicators (expert panel): These will take place online, with the final discussion taking place via (online) teleconference.

SELECTION OF PARTICIPANTS

ELIGIBILITY CRITERIA

Inclusion Criteria

Surveys of health and social care needs and the extent to which they are being met by current service provision: Any individual aged 18+ years that is on probation, in the community (including probation Approved Premises) in one of the Local Delivery Units selected for the study that probation staff believe has sufficient understanding of English to complete the survey, and capacity to provide informed consent

Online/telephone interviews: staff that have administered the surveys of health and social care needs.

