Service user panel focus group: Individuals aged 18+ with lived experience of the criminal justice system, including being on probation with sufficient understanding of English and capacity to consent to participate in the focus group.

Online surveys for development of quality indicators (expert panel): Individuals working in the health and justice arena - we will approach National Probation Service Health leads, and individuals working in appropriate roles in Clinical Commissioning Groups, Public Health England, the Ministry of Justice, Health and Wellbeing Boards (commissioners), and HM Inspectorate of Probation.

Exclusion Criteria

Surveys of health and social care needs and the extent to which they are being met by current service provision: Individuals aged less than 18 years, individuals with insufficient understanding of English to complete the survey, individuals who do not have capacity to provide informed consent.

Online/telephone interviews: people that have not been involved in administering the survey.

Service user panel focus group: Individuals aged less than 18 years, or without relevant lived experience, or insufficient understanding of English or capacity to consent to participate in the focus group.

Online surveys for development of quality indicators (expert panel): Individuals that are not working in appropriate roles in the health and justice arena.

Sampling

IMPROVING DATA COLLECTION (SURVEYS OF HEATLH AND SOCIAL CARE NEEDS)

The research team have worked with a probation service Divisional Director to identify probation Local Delivery Units that contain a mixture of urban and rural areas, including one Local Delivery Unit with an above average proportion of people on probation from BAME groups (to facilitate inclusion of these groups in the research responses). Probation staff have a list of everyone that is on the caseload and based in the community (including within Approved Premises) in these areas, which they will use to notify the research team of the number of surveys required, and to track who has participated in the survey, who has declined to participate, and when reminders have been given.

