All individuals in these areas will be invited to participate in the survey when they attend at probation premises, or by remote contact (telephone or online) if they attend less than once a month, or are not able to attend due to ongoing restrictions in relation to covid-19 - i.e. probation staff are not selecting participants, they are giving details of the study to all potential participants on the caseload.

An email will be sent via our probation co-applicant to all staff that may have played a role in administering the survey to ask for volunteers to participate in an online/telephone interview to provide feedback on what this was like.

DEVELOPING QUALITY INDICATORS

Page 14 of 25

The service user panel will be recruited by Revolving Doors staff and their Lived Experience Peer Researchers from those involved in their Lived Experience research.

The expert panel will be recruited by the Research Team. A National Probation Service Divisional Director is part of this team, and will invite National Probation Service Health Leads to participate if they wish to. The research team already have a list of potential participants based in the other key organisations listed earlier in this form that they can invite to participate based on their appropriateness due to their roles within the health and justice arena. The study has already been discussed with members of some of these organisations, who have been supportive of the research proposed.

Size of sample

We anticipate that there will be 3000-4000 people on probation across the Local Delivery Units, all of whom will be invited to complete a survey. We anticipate that we will achieve a minimum return rate of 10% but will aim to achieve a higher rate (likely to be between 33% and 50%). This should give sufficient data to be able to complete the analysis set out above. We would like 5-10 staff to take part in online/telephone interviews to provide feedback on this.

We aim to recruit 5-10 people with lived experience of the criminal justice system for the focus group, and 10-15 people in appropriate roles in the health and justice field for the expert panel. This should be a manageable number of individuals and give us sufficient data to gain insight into service user views and experiences, and to ensure that a range of appropriate organisations are represented on the expert panel.

Sampling technique

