After consent is taken, the survey can then be either self-completed with a member of probation staff present, or completed by a member of probation staff on the participant's behalf, with the staff member reading through it with the participant either face-to-face or via remote contact (e.g. phone/Microsoft Teams). This is to ensure that the study is as inclusive as possible. The survey will only be administered remotely if the participant has an appropriate (private) space in which to take part, and individuals will not be able to self-complete the survey and return it via email, as probation staff need to review the answers straight after it is completed.

Probation staff will use their judgement to select who has sufficient understanding of English to take part, and capacity to provide informed consent. It will be made clear to potential participants that taking part is voluntary and individuals

Page 15 of 25

are free to withdraw at any time, without giving any reason, and without their legal rights or relationship with probation being affected. However, as participation is anonymous it will not be possible to withdraw data once submitted, as the research team will have no way of identifying individual participants.

If a member of probation staff completes the survey with a participant, they will already be aware of their answers. If the participant self-completes it at a face-to-face appointment, they will then hand it back to a member of probation staff, who will immediately review the answers to check if they indicate any increased risk of harm to self or others (e.g. feeling suicidal). In all cases, after the responses have been read by probation staff, they will then be placed in a pre-addressed freepost envelope for return to the research team.

Potential participants in online/telephone interviews for feedback around administration of the survey will receive an information sheet and consent form attached to an email sent to all relevant staff via probation.

Potential participants in the service user panel will be approached by Revolving Doors and given an information sheet and consent form to read and complete prior to participating. They will be recruited via their Peer Researcher/Lived Experience network.

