4) Draft set of quality indicators produced from the findings from the above stages
Dago 10 of 25
Page 19 of 25 Developing data collection and quality indicators for probation - Protocol Draft Version 1 date 02.04.20

5) Second expert panel survey – the panel members will already have received an information sheet and consent form about this stage of the research at step 1, but will be asked to repeat consent here, following a reminder about the purpose of the survey.

6) Final discussion of quality indicators – participant will have seen information sheet and signed a consent form when completing the first expert panel survey, but will be reminded of the purpose of the discussion at the beginning of the conversation.

STUDY REGIMEN

IMPROVING DATA COLLECTION (SURVEYS OF HEATLH AND SOCIAL CARE NEEDS)

Individuals participating in this stage of the study will be asked to complete a consent form and a survey about their health and social care needs and the extent to which they are being met or to take part in a telephone/online interview (staff).

Surveys will be self-completed at probation premises, or completed over the phone or an online platform such as Microsoft Teams with answers being recorded by probation staff. They will contain guestions as follows:

- Demographic data: gender, ethnicity, age, (to be used as described in the analysis below)
- Past diagnoses: Have you ever been diagnosed with: a learning disability, a learning difficulty (e.g. dyslexia), ADHD, autism, personality disorder, a mental illness? Do you have any physical or mental health conditions or illnesses lasting, or expecting to last 12 months or more?
- Service use: GP registration and use, A&E attendance
- Met and unmet needs including for social care and physical health: collected on the CANSAS-P
- Substance misuse: alcohol use (collected on AUDIT-C), drug use (collected on DAST-10)
- Mental health and suicide prevention: collected on CORE-10 and CANSAS-P

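### Four purposively chosen Local Delivery Units cannot support inference on area characteristics in the planned mixed effects models

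*Protocol*

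**What the plan says.** Under DATA ANALYSIS, and in the same words in the study summary, the survey data are to be described and then modelled: mixed effects models "will be used to predict health and social care needs based on service user and area characteristics". The word area is not defined there. The protocol does not say whether LDU enters as a random or a fixed effect.

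STUDY SETTING fixes the areas: "Data will be collected across four probation Local Delivery Units containing a mixture of urban and rural areas". The Sampling section shows that they were picked on purpose with a probation Divisional Director, "including one Local Delivery Unit with an above average proportion of people on probation from BAME groups".

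Under Size of sample: "We anticipate that there will be 3000-4000 people on probation across the Local Delivery Units". All are to be invited, with a minimum return of 10% and 33% to 50% thought likely. The section then concludes: "This should give sufficient data to be able to complete the analysis set out above". It counts respondents and does not mention the number of areas.

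The demographic items listed under STUDY REGIMEN are gender, ethnicity and age. No postcode, office or other area item is listed. Under RECRUITMENT, returns are anonymous, so that "the research team will have no way of identifying individual participants".

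**The concern.** A characteristic of an area is measured once per area. The information about its effect comes from the number of areas, and respondents add to it only by making each area's mean more precise. With four LDUs, an LDU-level characteristic takes at most four values, and the between-LDU variance against which it is judged has at most 3 degrees of freedom. Because the LDUs were chosen for their profile, any such characteristic is also hard to separate from everything else that distinguishes that LDU.

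The stated purpose is to support commissioning. A chance difference between two pairs of LDUs, reported as an effect of rurality or caseload composition, would be easy to misread as something that applies elsewhere.

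**Working it through.** **Inputs from the protocol.** Four LDUs; 3000 to 4000 invited; return 10% (minimum) or 33% to 50% (likely). The protocol gives no power, precision or intraclass correlation (ICC) for the models, so there is no stated figure to reproduce.

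**Assumptions, not in the protocol.** ICC 0.01, 0.02 or 0.05; continuous outcome; LDUs of equal size; two-sided 5% level; one binary LDU-level predictor, two LDUs against two.

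**Step 1: returns per LDU.**
- 10%: 300 to 400 in total, divided by 4 = 75 to 100.
- 33%: 990 to 1320, divided by 4 = about 250 to 330.
- 50%: 1500 to 2000, divided by 4 = 375 to 500.

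**Step 2: degrees of freedom.** With k LDUs and p LDU-level predictors, k − 1 − p remain. For k = 4 this is 3 with none, 2 with one and 0 with three. The two-sided 5% critical value on 2 df is 4.30, not 1.96.

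**Step 3: between-LDU variance, best case.** Treat the LDU means as known without error. The 95% limits are the estimate times (k − 1)/χ² at the 97.5% and 2.5% points on k − 1 df. For k = 4 these are 0.32 and 13.9 times the estimate; for k = 30 they would be 0.63 and 1.81. Unlimited respondents would not narrow the interval for four LDUs.

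**Step 4: false-positive rate.** Balanced random-intercept model, 20,000 runs per setting, no true area effect:

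| ICC | Respondents per LDU | REML, Wald z | ML, Wald z | t on 2 df |
|---|---|---|---|---|
| 0.01 | 75 | 8.5% | 11.7% | 4.7% |
| 0.01 | 500 | 16.0% | 24.7% | 4.7% |
| 0.02 | 75 | 11.4% | 16.4% | 5.0% |
| 0.02 | 500 | 17.8% | 27.6% | 4.8% |
| 0.05 | 75 | 15.2% | 23.4% | 5.1% |
| 0.05 | 500 | 19.0% | 29.6% | 5.1% |

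The limit for very large LDUs can be checked by hand. For t on 2 df, P(|t| > x) = 1 − x/√(2 + x²).
- REML: x = 1.96, giving 1 − 1.96/√5.842 = 18.9%.
- ML divides the residual sum of squares by 4 instead of 2, so x = 1.96/√2 = 1.386, giving 1 − 1.386/√3.921 = 30.0%.

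The simulated rates climb towards these limits, so a higher return rate makes the Wald test worse. A one-against-three split gave the same picture. With 30 areas of 50 respondents, the Wald rates were 5.6% to 7.3%.

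**Step 5: power of the valid test.** For a difference of d standard deviations, SE = √[ICC + (1 − ICC)/m], with m respondents per LDU. Power comes from the noncentral t on 2 df with noncentrality d/SE. Example: ICC 0.01, m = 75, d = 0.5 gives SE = √0.0232 = 0.152, noncentrality 3.28 and power 44%.

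| ICC | m = 75 | m = 250 | m = 500 |
|---|---|---|---|
| 0.01 | 44% | 60% | 66% |
| 0.02 | 34% | 43% | 46% |
| 0.05 | 22% | 24% | 25% |

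For d = 0.3 the range is 11% to 34%.

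**Step 6: service-user predictors.** Individual ethnicity was checked with an assumed minority share of 10%, 10%, 10% and 40% in the four LDUs, using REML. The bias of the ethnicity coefficient was at most 0.006 SD and its type I error 4.2% to 6.2%. With LDU as a fixed effect the type I error was 4.3% to 5.7%.

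**The case against.** **The test is not specified.** The protocol names neither ML, REML nor a Wald z-test, and an SAP could choose a small-sample method. This stands in part: the rates in step 4 describe default software output, and the 2-df t-test does hold 5%. But an SAP cannot add areas, so it can only exchange an invalid test for a weak one. The number of areas and the aim of predicting from area characteristics are both fixed in the protocol.

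**Area may mean something smaller than an LDU.** The LDUs are described as containing both urban and rural parts, so rurality could vary within an LDU. This is fair. However, no finer unit is named or listed among the survey items, and anonymous returns would make it hard to add one later. It is a reason to define area, and it does not make the current plan adequate.

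**Readings that go too far.** A reader might infer four stronger things.
- *The whole mixed model fails, and ethnicity becomes mixed up with the LDU chosen for its caseload.* Step 6 shows otherwise. Individual ethnicity is estimated mostly within LDUs.
- *The between-LDU variance will usually be estimated as zero.* That is a problem of the 10% floor. Without a covariate, the simulated share of zero estimates was 8% to 37% at 75 to 100 per LDU, 2% to 16% at 250 and 1% to 8% at 500. Under ML at the likely return it was about 1% to 23%.
- *Area effects cannot be validly estimated at all.* Point estimates exist and the 2-df test is valid.
- *The LDU is not attached to the record.* The protocol lists questions put to participants and is silent on administrative codes. An LDU code would not breach anonymity, and silence does not show that it is absent.

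**Conclusion.** The point holds for inference on LDU-level characteristics. With one such predictor, default Wald tests would reject a true null about 12% to 30% of the time (ML) or 8% to 19% (REML), and a better return rate raises these figures. The valid alternative has 22% to 66% power for a difference as large as half a standard deviation. The sufficiency statement under Size of sample is therefore not supported for area predictors.

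These figures rest on assumed ICCs of 0.01 to 0.05, equal LDU sizes and a continuous outcome; logistic models were not simulated. The limits on degrees of freedom do not depend on the ICC.

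Service-user effects and the descriptive analysis of prevalence and met need are unaffected. Since the primary outcome is that descriptive overview, the severity is moderate.

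**What to change.** Change the modelling sentence under DATA ANALYSIS and in the study summary:

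1. Enter LDU as a fixed effect (three indicators) alongside the service-user predictors.
2. Drop inferential claims about LDU-level characteristics, and report four LDU-specific estimates descriptively.
3. Define area. Keep a random effect or area predictors only for a recorded finer unit, such as office, if there are enough units.
4. State that an LDU code and, if feasible, an office code is recorded on each form. This has to be settled before fieldwork.
5. Limit the sufficiency statement under Size of sample to the descriptive and service-user analyses.

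The cost is a change of wording and, if not already planned, a code printed on the form. What is given up is inference on area-level predictors, which four LDUs could support only very weakly.

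If that inference matters to the sponsor, the alternatives are more LDUs or a finer recorded unit, and both cost more.
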